Study Enrollment and Consent: Postpartum nurses and providers will be invited to participate in individual in-depth interviews about their perceptions of IPP-HPV. All participants will receive informed consent (see attached) and a \$25 VISA card will be provided as an incentive to providers that participate.

Sampling: We will aim to have a purposive sample with representation by provider type and clinical setting/location.

1.3.3 Data collection: The in-depth individual interviews will be conducted using a semi-structured guide (see attached) based on Consolidated Framework for Implementation Research (CFIR) constructs. We will focus on CFIR constructs belonging to domains which we consider to be most relevant to IPP-HPV implementation from the providers' perspective: *Intervention Characteristics* (e.g., perceived advantages and adaptability of the intervention), the *Inner Setting* (e.g., structural and cultural contexts within the clinical setting), and *Characteristics of Individuals* (e.g., knowledge and beliefs about the intervention).

1.3.4 Data analysis: Recorded interviews will be transcribed and transcripts analyzed using standard analytic methods for qualitative data as described above (see Aim 2). Provider receptivity of IPP-HPV and perceptions of patient acceptance will be categorized by themes. Perceived barriers to and facilitators of IPP-HPV will be described and will further inform future implementation of IPP-HPV. Demographic data about postpartum providers will be tabulated. Quantitative data from the pre- and post-intervention provider surveys will be tabulated and differences compared using bivariate analysis.

1.4 Specific Aim 3

To assess the uptake and effectiveness of a Pilot Quality Improvement Program to increase HPV vaccine uptake (IPP-HPV) for Yale New Haven Hospital (YNHH) Women's Center and Center for Women's Health and Midwifery (CWHM) postpartum patients ≤ 26 years of age who deliver at YNHH

York Street Campus (YSC) or Saint Raphael Campus (SRC).

1.41 **Study participants:** Women’s Center and CWHM postpartum patients ≤ 26 years of age who have received less than 3 doses of the HPV vaccine prior to delivery and who deliver at YNHH YSC or SRC during the two years of the IPP-HPV Program as well as Women’s Center and CWHM postpartum patients ≤ 26 years of age who delivered at YNHH YSC/SRC in the year preceding implementation of the IPP-HPV Program.

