We will obtain data on receipt of subsequent doses of vaccine and on completion of the 3-dose series of the vaccine by medical chart review. Dates of receipt of HPV vaccine, date of postpartum visit, and data on whether a dose of HPV vaccine was due at the postpartum visit and, if so, whether dose was received will be recorded. Data on the need for and receipt of postpartum Tdap, influenza and rubella vaccines will also be obtained from medical chart review for comparison. Demographic and clinical information will also be obtained. Historical data on the HPV vaccination history of all WC patients \leq 26 years old who delivered in the 12 months prior to implementation of IPP-HPV will also be collected for comparison of their rates of vaccine series completion (from outpatient administration) within 30 months of delivery.

144

Data analysis: We will tabulate measures as follows:

- IPP-HPV Acceptance: Proportion of eligible patients agreeing to receive a dose of vaccine
- HPV Vaccine Administration: Proportion of eligible patients that agree to be vaccinated who actually receive dose of vaccine as an inpatient.
- Barriers to vaccination: descriptive data on potential barriers to receiving the vaccine postpartum
- Other vaccines: Proportion of eligible patients due for Tdap, influenza or MMR vaccines and proportion that receive each

To assess the effectiveness of the pilot IPP-HPV immunization program we will tabulate the proportion of postpartum women eligible for the vaccine who receive a dose of HPV vaccine, the proportion of participants that need 1, 2, or 3 vaccine doses that receive the respective number of doses within up to 30 months of postpartum discharge, the proportion of all participants that complete the vaccine series within 12 months and within 30 months, and the proportion of study participants that complete the vaccine series within 12 months and within 30 months that received IPP-HPV.

Multivariable logistic regression will be used to determine predictors of inpatient postpartum HPV vaccine uptake and of vaccine completion (e.g., age, parity, race, ethnicity). The difference in proportion of women who complete the 3-dose series within 12 months and within 30 months of postpartum discharge in the study cohort and in the group of Women's Center patients who delivered in the 12 months prior to implementation of IPP-HPV will be compared using chi square analysis.

1.5 Specific Aim 4

151 Study participants:

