6. **Subject classification:** Check off all classifications of subjects that will be specifically recruited for enrollment in the research project. Will subjects who may require additional safeguards or other considerations be enrolled in the study? If so, identify the population of subjects requiring special safeguards and provide a justification for their involvement.

 Children	 Healthy	 Fetal material, placenta, or dead fetus
 Non-English Speaking	 Prisoners	 Economically disadvantaged persons
 Decisionally Impaired	 Employees	 Pregnant women and/or fetuses
 Yale Students	 Females of childbearing potential	

NOTE: Is this research proposal designed to enroll children who are wards of the state as potential subjects? **Yes** **No**

7. **Inclusion/Exclusion Criteria:** What are the criteria used to determine subject inclusion or exclusion?

Specific Aim 1: Patient Qualitative Interviews

Inclusion:

- Women participating in the IPP-HPV Quality Improvement Program:
 - Postpartum YNHH Women's Center and CWHM patients
 - ≤ 26 years at time of delivery who deliver at YNHH YSC or SRC
 - Have not already received 3 doses of the HPV vaccine at time of delivery
- Fluent in English or Spanish
- Able and willing to provide consent

Specific Aim 2: Provider Qualitative Interviews

Inclusion:

- YNHH inpatient postpartum nurses or Women's Center outpatient postpartum nurses or inpatient or outpatient obstetric providers affiliated with the Women's Center or Center for Women's Health and Midwifery
- Able and willing to provide consent

Specific Aim 3: Medical Records Review

Inclusion:

- Yale New Haven Hospital (YNHH) Women's Center and Center for Women's Health

and Midwifery (CWHM) postpartum patients

- ≤ 26 years of age
- Delivered at YNHH York Street Campus (YSC) or Saint Raphael Campus (SRC) in the first year of the IPP-HPV program or in the one year preceding implementation of the program

Specific Aim 4:

Observational Workflow Analysis

Inclusion:

- YNHH (YSC or SRC) inpatient postpartum nurses or inpatient obstetric providers

Provider/Staff Qualitative

Interviews Inclusion:

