To assess the effectiveness of the pilot IPP-HPV immunization program we will tabulate the proportion of postpartum women eligible for the vaccine who receive a dose of HPV vaccine, the proportion of participants that need 1, 2, or 3 vaccine doses that receive the respective number of doses within 12 months of postpartum discharge, the proportion of all participants that complete the vaccine series within 12 months, and the proportion of study participants that complete the vaccine series within 12 months that received IPP-HPV.

Multivariable logistic regression will be used to determine predictors of inpatient postpartum HPV vaccine uptake and of vaccine completion (e.g., age, parity, race, ethnicity). The difference in proportion of women who complete the 3-dose series within 12 months of postpartum discharge in the study cohort and in the group of Women's Center patients who delivered in the 12 months prior to implementation of IPP-HPV will be compared using chi square analysis.

Specific Aim 4:

All workflow analysis and individual interviews and will be recorded and subsequently transcribed. We will analyze transcripts and determine common themes and priority domains. Standard analytic methods for qualitative data will be employed.¹⁵ A codebook will be developed based on deductive (theory-driven) constructs from the interview guide and applied to a subset of transcripts. Concordance will be measured and discrepant codes resolved by adjudication using software for qualitative research. We will identify and discuss initial themes and identify inductive

(data-driven) codes. The identification of inductive codes will continue with subsequent coding in an iterative manner. The coded data will be used to iteratively develop process maps for each vaccine and to identify gaps in the process to guide subsequent observations.⁵⁵ The maps will also indicate process variations and identify steps in which EMR tools are utilized.

Specific Aim 5:

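### Aim 3 limits prior HPV doses in the program cohort but not in the prior-year comparator, so the completion chi-square is biased in a direction the plan leaves open

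*Combined protocol and SAP*

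**What the plan says.** - **Section I.3, 1.41 (Aim 3 participants), program cohort.** Women of the two clinics, aged 26 or under, "who have received less than 3 doses of the HPV vaccine prior to delivery and who deliver at YNHH YSC or SRC". Section I.5 uses the same wording.
- **Same sentence, comparator.** Women of the same clinics and ages "who delivered at YNHH YSC/SRC in the year preceding implementation of the IPP-HPV Program". The group is defined afresh, with no dose limit. I.5 again has the same structure.
- **1.43 (data collection), prior year.** "Historical data on the HPV vaccination history of all WC patients" in the age group are to be collected, to compare rates of "vaccine series completion (from outpatient administration) within 30 months of delivery".
- **Section I.7, Aim 3 inclusion list.** Delivery "in the first year of the IPP-HPV program or in the one year preceding implementation of the program", with no dose limit for either period. This conflicts with 1.41 and I.5 on who is in the program cohort.
- **Section I.7, Aim 1 list.** This describes who is in the program itself: women who "Have not already received 3 doses of the HPV vaccine at time of delivery".
- **1.44 and Section I.12 (analysis).** Completion in the study cohort and in Women's Center "patients who delivered in the 12 months prior to implementation of IPP-HPV will be compared using chi square analysis". The 1.44 text uses 12 and 30 months after discharge; Section I.12 uses 12 months only. Neither states a denominator. A separate tabulation, "the proportion of participants that need 1, 2, or 3 vaccine doses that receive the respective number of doses", is confined to women still needing doses, but the chi-square is not tied to it.

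**The concern.** A woman with three doses before delivery cannot be in the program cohort of 1.41, but she can be in the comparator. The plan does not say whether she is then dropped, counted as a completer, or kept in the denominator as a non-completer. The time limit on completion fixes when the window ends, not when it starts.

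The last two choices bias the comparison in opposite directions even if the program does nothing. Kept as non-completers, these women pull the historical rate down and make the program look effective. Counted as completers, they push it up, which can make the program look harmful or hide a real gain. Since the rule is unwritten, it could be settled after the results are seen. The logistic regression in the same section is for predictors of uptake and completion and has no stated cohort term, so it does not replace this test.

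**Working it through.** The plan has no figure to reproduce. It gives 700 charts for Aim 3 (Section III.1) without a split between cohorts, alpha, power or effect size. What follows sizes the problem under labelled assumptions.

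**Inputs**
- q = share of the comparator already complete at delivery. Not given for these clinics. The Background cites 13% completion at ages 18–26; it is used for orientation, with 5% to 20% as the range.
- p = completion among women still needing doses. Assumed 10% to 20%, the same in both periods when there is no effect.
- Charts: 700, split 350/350 (assumed), or 467/233 (assumed) if the program cohort spans two years as in 1.41. I.5 and I.7 say the first year only.
- Test: uncorrected chi-square, two-sided 5% (assumed). Rejection probabilities come from exact binomial enumeration and are split by direction, so the nominal rate is 2.5% each way.

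**Comparator rate under each rule, no program effect**
- Dropped: p, so bias 0.
- Kept as non-completers: (1−q)p, so bias (program minus comparator) = +qp.
- Counted as completers: q+(1−q)p, so bias = −q(1−p).

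**At q = 13%, p = 20%**
- Non-completers: 0.87 × 0.20 = 17.4%; bias 0.13 × 0.20 = +2.6 points.
- Completers: 0.13 + 0.174 = 30.4%; bias −0.13 × 0.80 = −10.4 points.

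**Chance of a false significant result, no program effect**

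| q | p | For the program, kept as non-completers (350/350; 467/233) | Against the program, counted as completers (350/350; 467/233) |
|---|---|---|---|
| 5% | 10% | 4.1%; 3.6% | 44.6%; 41.9% |
| 5% | 20% | 5.2%; 4.7% | 24.7%; 23.2% |
| 13% | 10% | 8.5%; 7.2% | 99.1%; 98.3% |
| 13% | 20% | 14.0%; 12.3% | 89.0%; 85.5% |
| 20% | 10% | 14.9%; 12.4% | >99.9%; >99.9% |
| 20% | 20% | 28.0%; 24.2% | 99.7%; 99.4% |

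Over this grid the bias runs from +0.5 points (0.05 × 0.10) to +4.0 (0.20 × 0.20) under the first coding, and from −4.0 (0.05 × 0.80) to −18.0 (0.20 × 0.90) under the second.

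**If the program works.** Take a true rise from 20% to 30% among women in need (assumed), q = 13%. With completer coding the test sees 30.0% vs 30.4%, and the chance of detecting the gain is 1.9% at either split. With the comparator restricted to women in need it is 84.0% (350 vs about 304) or 78.0% (467 vs 203).

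**After restricting the comparator.** At q = 13%, p = 20%, 350 vs 304 and no effect, false results are 2.5% for and 2.7% against the program, close to nominal.

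**If I.7 governed instead.** Leave both periods unrestricted, with the same q and one coding. The bias under no effect disappears, but a true difference shrinks by 1−q: 10 points become 8.7. At 350/350, power is 80.0% with non-completer coding (26.1% vs 17.4%) and 68.0% with completer coding (39.1% vs 30.4%). The same charts restricted in both cohorts (304/304) give 81.6%.

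**The case against.** The strongest reply is that the text leans towards completion after delivery. Record review covers the 30 months after delivery, comparator completion is tied to outpatient administration in that window, and an adjacent measure is defined by doses still needed. On that reading the 89.0% and 1.9% figures rest on the less likely coding. This is fair on emphasis, and the non-completer results are the ones to read first. But the lean is not a rule. Even if it is accepted, nothing removes already-complete women from the comparator denominator. They become women who cannot meet the endpoint, in one cohort only, and that favours the program.

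A second reply is that the investigators could restrict the comparator themselves, or apply I.7 to both periods. Either would remove the bias under no effect, the I.7 route only if the already-complete share is equal in the two years. But both depart from 1.41 and I.5 as written, and the plan commits to neither.

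Third, the size is assumed. At q = 2% and 350/350, false results are only 3.1–3.4% for the program and 7.5–11.6% against it. In the other direction, the Background cites 40% completion among adolescents, and the cohort can include patients under 18. At q = 40% and p = 10%, a normal approximation gives about a 50% chance of a false result for the program under non-completer coding. The documents do not show where in this span the clinics lie.

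Finally, this is a pilot quality improvement evaluation with no stated alpha, so 2.5% is a conventional benchmark. That limits the gravity of the point, but effectiveness is in the wording of Aim 3.

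**Conclusion.** The concern holds. As 1.41 and I.5 define the cohorts, the completion chi-square compares women who still need doses with a group that may include women who do not. It is then biased whichever way the already-complete women are coded, and the sign depends on a choice the plan does not state.

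That the denominators differ follows from the text alone. The size depends on q, p, the assumed true effect and the chart split, none of which the documents give for these clinics. Under the coding the text leans towards, the problem is moderate and negligible only if q is very small. Under the other coding it would dominate the result. This should be fixed before the comparison is run.

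**What to change.** 1. In 1.41, I.5 and I.7, state one limit for both cohorts: fewer than 3 documented HPV doses before delivery, taken from the same chart source.
2. In 1.44 and Section I.12, name that group as the denominator of the chi-square.
3. Count a series as completed only when the completing dose is given after delivery, including the inpatient postpartum dose.
4. Prior-year histories can still be collected on all women and then restricted for the test.

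If the sponsor prefers the I.7 population, the plan should say so in all three places and state one coding for both periods, accepting the diluted difference and the assumption of equal already-complete shares.

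While editing, reconcile the comparator's clinics: 1.41 names both, whereas the 1.43 and chi-square wording names the Women's Center only. No bias is claimed from that here.

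The cost is wording and a smaller comparator: 350 becomes about 304 at q = 13% (350 × 0.87). No new data are needed, since 1.43 already abstracts the administration date and series number of each dose.

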If Yes, please answer questions a through c and note instructions below.

a. Does your YNHH privilege delineation currently include the **specific procedure** that you will perform? Yes No

b. Will you be using any new equipment or equipment that you have not used in the past for this procedure? Yes No

c. Will a novel approach using existing equipment be applied? Yes No

If you answered "no" to question 4a, or "yes" to question 4b or c, please contact the YNHH Department of Physician Services ([name]) for prior approval before commencing with your research protocol.

IMPORTANT REMINDER ABOUT RESEARCH AT YNHH

Please note that if this protocol includes Yale-New Haven Hospital patients, including patients at the HRU, the Principal Investigator and any co-investigators who are physicians or mid-level practitioners (includes PAs, APRNs, psychologists and speech pathologists) who may have direct patient contact with patients on YNHH premises must have medical staff appointment and appropriate clinical privileges at

YNHH. If you are uncertain whether the study personnel meet the criteria, please telephone the Physician Services Department at [contact]. **By submitting this protocol as a PI, you attest that you and any co-investigator who may have patient contact has a medical staff appointment and appropriate clinical privileges at YNHH.**

SECTION I: RESEARCH PLAN

1. **Statement of Purpose:** State the scientific aim(s) of the study, or the hypotheses to be tested.

Specific Aims

- Aim 1: To evaluate receptivity and concerns of postpartum women with receiving the HPV vaccine during the inpatient postpartum admission as part of the Inpatient Postpartum HPV Immunization Quality Improvement Program (IPP-HPV) [see appendix].
- Aim 2: To evaluate receptivity and concerns of healthcare providers with inpatient postpartum HPV immunization as part of IPP-HPV and to identify facilitators of and barriers to its implementation.
- Aim 3: To assess the uptake and effectiveness of a Pilot Quality Improvement Program to increase HPV vaccine uptake (IPP-HPV) for Yale New Haven Hospital (YNHH) Women's Center and Center for Women's Health and Midwifery (CWHM) postpartum patients ≤ 26 years of age who deliver at YNHH York Street Campus (YSC) or Saint Raphael Campus (SRC).
- Aim 4: To identify the processes utilized to integrate delivery of vaccines that are currently administered routinely during inpatient postpartum care

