Investigators have found that in a predominantly Hispanic population of postpartum women in southeast Texas with a low rate of HPV immunization, there was a high degree of willingness to receive the vaccine if offered free of charge.¹⁰ One small study evaluated inpatient postpartum HPV immunization (IPP-HPV) in a selective patient population and, although it was successful with 95% uptake of the HPV vaccine during the postpartum admission, full vaccine series completion was 30%.¹¹ With attention to outpatient followup infrastructure, Berenson et al recently have shown that a standard of care inpatient postpartum vaccination program can increase initiation and completion rates.¹² Studies to date have not evaluated the process of clinical implementation of IPP-HPV nor identified facilitators of or barriers to the intervention to improve its effectiveness. Evaluating the implementation process systematically to investigate and address bottlenecks is critical for the successful promotion and integration of new approaches in the delivery of evidence-based practices.

The purpose of the proposed pilot study is to assess the implementation of IPP-HPV immunization at YNHH and to identify potential barriers to and facilitators of this intervention to optimize its feasibility and effectiveness. It is imperative that we develop innovative interventions to achieve comprehensive utilization of this highly effective vaccine to reduce rates of HPV infection, lower rates of cervical and other HPV-associated cancers, and address cancer disparities.

References

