1.1 Overview

We propose a mixed methods study that will evaluate the implementation process of the Inpatient postpartum HPV Immunization Quality Improvement Program (IPP-HPV) using 9-valent HPV vaccine for postpartum YNHH Women's Center patients to increase the rate of HPV vaccination. We will also study the effectiveness of the program to improve HPV vaccine series completion. The study will utilize qualitative patient and provider interviews as well as a medical records for data collection to identify facilitators of and barriers to successful implementation of IPP-HPV. Study of the quality improvement program may help translate what has been a missed opportunity to vaccinate into a potential national model for a public health intervention that could prevent cervical cancer.

1.2 Specific Aim 1

To evaluate receptivity and concerns of postpartum women with receiving the HPV vaccine during the inpatient postpartum admission as part of the Inpatient Postpartum HPV Immunization Quality Improvement Program (IPP-HPV).

121 **Study participants:** Patients participating in the IPP-HPV Program and fluent in either English or Spanish will be eligible to enroll in this qualitative study.

122 **Study design:**

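### Aim 3 concerns a program to increase HPV vaccine uptake, but only 3-dose completion is compared with the pre-program year; no planned analysis can show that uptake rose

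*Combined protocol and SAP*

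**What the plan says.** Section I.1 and Section 1.4 state Aim 3 in part as "To assess the uptake and effectiveness of a Pilot Quality Improvement Program to increase HPV vaccine uptake (IPP-HPV". The overview (1.1) gives raising the rate of HPV vaccination as the program's purpose, and then adds "We will also study the effectiveness of the program to improve HPV vaccine series completion".

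The Aim 3 data analysis (1.44) tabulates acceptance, inpatient administration, receipt of a dose by eligible women, and receipt of the 1, 2 or 3 doses still needed. A logistic regression looks for predictors of inpatient uptake and of completion; its examples are age, parity, race and ethnicity.

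The pre-program year enters one comparison. Its outcome is "The difference in proportion of women who complete the 3-dose series within 12 months and within 30 months of postpartum discharge". The comparator for the program cohort is a group from the Women's Center, namely those "who delivered in the 12 months prior to implementation of IPP-HPV will be compared using chi square analysis". The data collection section gives the purpose of the historical data: they "will also be collected for comparison of their rates of vaccine series completion (from outpatient administration) within 30 months of delivery". Section I.12 carries the same comparison in a shorter form, "The difference in proportion of women who complete the 3-dose series within 12 months of postpartum discharge in the study cohort".

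**The concern.** An increase needs a comparator. The plan has one, the year before the program, but uses it for completion only. Receipt of a dose, the outcome the program acts on most directly, has no between-period analysis.

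Two conclusions are then out of reach. A high proportion dosed under the program does not show a rise, because some of those women might have received the dose as outpatients anyway. And if more women receive a dose but few finish the series, the completion test may show little, with no planned analysis to register the gain. Section V says the results should document effectiveness and support expansion, so the net gain in vaccination matters to the decision the study is meant to inform.

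**Working it through.** **Step 1. Which outcomes have a comparator?**

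| Outcome in 1.44 | Planned handling | Compared with pre-program year? |
|---|---|---|
| Acceptance; inpatient administration | tabulated | no |
| Receipt of a dose | tabulated | no |
| Receipt of the 1, 2 or 3 doses needed | tabulated | no |
| Predictors of uptake and completion | logistic regression | no period or program term named |
| 3-dose completion | chi-square | yes: 12 and 30 months in 1.44, 12 months in I.12 |

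The gap follows from the text and needs no arithmetic.

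**Step 2. Are the data there?** Section 1.42 reviews the charts of all patients in 1.41, which includes the pre-program year, for 30 months after delivery. Section 1.43 lists the date and rank of each dose. An any-setting comparison needs no new variable.

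**Step 3. Can completion stand in for uptake?** This is an illustration only. The plan's figure of 700 charts (Section III.1) cannot be reproduced: no alpha, power, effect size, expected rates or split between periods is given.

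Inputs:
- From the Background: 30% initiation and 13% completion in women aged 18-26; 95% inpatient uptake and 30% completion in one small postpartum study.
- Assumed: n = 350 charts per period, two-sided alpha 0.05, the 30% and 13% as baselines, and a rise in at-least-one-dose receipt to 50%.

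Power = Φ[(d − 1.96·SE0)/SE1], where d = p2 − p1, p̄ = (p1 + p2)/2, SE0 = √(2p̄(1 − p̄)/n) and SE1 = √(p1(1 − p1)/n + p2(1 − p2)/n).

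- **At least one dose, 30% to 50%:** d = 0.200, SE0 = 0.0370, SE1 = 0.0363. The argument of Φ is 3.51; power is above 99%.
- **Completion, if starters finish at 30/95 = 32%:** p2 = 0.50 × 0.316 = 0.158, d = 0.028, SE0 = SE1 = 0.0265. The argument is −0.91; power is about 18%.
- **Completion, if starters finish at 13/30 = 43%:** p2 = 0.50 × 0.433 = 0.217, d = 0.087, SE0 = 0.0286, SE1 = 0.0284. The argument is 1.08; power is about 86%.

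The same uptake gain may be nearly invisible or quite visible in the completion test, depending on follow-through, which is unknown here.

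**Step 4. Would the added comparison need more charts?** From a 30% baseline, the smallest rise detectable with 80% power is 10.1 points at 350/350 and 10.8 points at 233/467. For completion from 13% it is 8.0 and 8.6 points. The second split allows for two program years (1.41) against one pre-program year; Sections I.5 and I.7 speak of the first program year only. On these assumptions 700 charts suffice for a rise of about 10 to 11 points.

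**The case against.** The strongest reply is that the plan is coherent as it stands: uptake is described, effectiveness is tested, and 1.1 names series completion when it speaks of effectiveness. On that reading, increasing uptake describes what the program is for and is not a hypothesis. Much of this stands. Completion is a proper outcome for a 3-dose regimen, and in the small study cited the shortfall lay in completion, not inpatient uptake. But Aim 3 names uptake alongside effectiveness, and describing uptake in one period cannot show that the program raised it.

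A reader might go further and infer that the program is never contrasted with usual outpatient care. The documents do not support that: historical completion comes from outpatient administration, so the completion test is such a contrast. For a woman with two prior doses, the inpatient dose itself completes the series. The documents give no distribution of prior doses, so it cannot be said that completion rests mostly on later visits. If inpatient doses only replaced outpatient ones, the completion test would also tend to show no gain.

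A reader might also subtract an assumed pre-program proportion from an inpatient uptake figure and call the difference the true gain. The documents give no such baseline, and the subtraction would mix an inpatient outcome with an any-setting outcome over a different window.

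Finally, 1.41 counts pre-program women as participants, so the tabulation of dose receipt might be read as covering both periods. The wording leaves that open, but no comparison is specified.

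**Conclusion.** The point holds as a gap in the planned comparisons. As written, Aim 3 can report how many women received a dose and can test whether completion changed. It cannot show that uptake rose, or tell added doses from doses brought forward. The completion analysis is unaffected.

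The consequence is conditional. The 18% and 86% rest on the assumed split, alpha and size of rise, and on rates from other populations; the 30% initiation rate is not post-delivery receipt among women with fewer than 3 doses. They show that completion may be a poor proxy for uptake, not that it will be. Nor do the documents show that at-least-one-dose receipt must become the main measure; that ranking is a trade-off the investigators may decide either way. The change is worth making because it answers a question the aim poses, from data already to be abstracted.

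**What to change.** In 1.44 and I.12, add a between-period comparison of the proportion of women with fewer than 3 doses at delivery who receive at least one HPV dose in any setting, from delivery to 12 months and to 30 months. Report it beside completion, which stays as planned. Doses received out of those still needed can be added descriptively.

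Three details should be settled in the text:
- **Denominator.** Apply the fewer-than-3-doses restriction to both cohorts. Section 1.41 does not state it for the pre-program year. Women already fully vaccinated have no dose to receive, so including them there would lower the pre-program proportion and exaggerate any rise.
- **Clinics.** Use the same clinics in both periods. Section 1.41 includes both the Women's Center and CWHM, whereas the historical-data sentence and the chi-square comparison name Women's Center patients only.
- **Setting and start of window.** Count doses from any setting, starting at delivery. Inpatient vaccine was not routinely available before the program, so inpatient receipt alone is no useful contrast. A window starting at discharge, read strictly, would leave out the inpatient dose.

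The cost is protocol wording, one more between-period comparison to report, and the work of settling the historical denominator from data already abstracted. No new variable is needed and, on the assumptions above, no more charts.
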